### *Inclusion criteria*

Several different inclusion criteria are possible and will be assessed in the first primary objective. Individuals will be included if they reside in the catchment area or are active members in the health system's insurance plan and then will be evaluated against each of the following criteria.

- 1) Any individual who is otherwise eligible and had a telephone-based care visit, an ambulatory encounter, an urgent care encounter, an emergency department encounter, or an inpatient encounter with the health system in the 12 months prior to the start of influenza season. Ambulatory encounters include office-based visits to a primary care practice office (including but not limited to general pediatrics, general internal medicine, med-peds, obstetrics/gynecology, or general family medicine), or office-based visits to a medical specialty office (including but not limited to cardiology clinic, diabetes clinic, rehabilitation clinic, gastrointestinal specialist, etc.).

- 2) Any individual who is otherwise eligible and had an ambulatory encounter (to a primary care practice office or a medical specialty office) or an inpatient encounter with the health system in the 12 months prior to the start of influenza season.
- 3) Any individual who is otherwise eligible and had an ambulatory encounter with the health system in the 12 months prior to the start of influenza season.
- 4) Any individual who is otherwise eligible and had an encounter to a primary care practice office with the health system in the 12 months prior to the start of influenza season. General practice encounters include office-based visits to a general pediatrics, general internal medicine, med-peds, obstetrics/gynecology, or general family medicine clinic.
- 5) **[For closed health systems only]** For health systems where individuals can have an active membership in the health system, an additional inclusion criterion will be considered. The inclusion criteria will be any individual who was an active member in the health system for the period of 12 months before the start of influenza season (or was born and became a member during the 12 months prior to the start of or during the influenza season) and were active members until the end of influenza season, death, or disenrollment, whichever occurred first.

For a single season, such as the 2017/18 season, the cohorts defined by the different inclusion criteria will be assessed in terms of the number, the demographic characteristics, the frequency of subsequent medical care, and the frequency of respiratory hospitalizations among cohort members (Appendix C). The definition of “medical care” to use will be determined by joint consensus among the collaborating sites prior to extracting data for the interim and final datasets.

### ***Exclusion criteria***

Individuals will be excluded from the seasonal cohorts if they are not active members of the health system or they resided outside of the catchment area of the health system for the entire 12-month period before the start of influenza season. Active membership can be determined based on enrollment in the health system. Catchment area may be known or approximated based on prior studies or other surveillance activities that the health system is engaged in. Catchment area can also be determined starting first with the counties surrounding the hospitals and then be further refined using information on county of residence, selecting the counties that unique patients most frequently live in.

### **5.3 Observation Time during Influenza Season**

For the primary objective of estimating the incidence of influenza-associated respiratory hospitalizations and ARI outpatient encounters, the person-time at risk for the underlying cohort will be needed. Person-time at risk for influenza will be calculated for all individuals in the seasonal retrospective cohorts. Observation time for a given season will start on the day that influenza season begins, September 1 of each year. For the same season, observation time will end on the day of death, disenrollment, move away from the catchment area, or the end of the influenza season (May 31), whichever occurs first. The total observation time, person-time, is then the difference between the start and end of observation. For analyses, observation time may be restricted to a shorter period of time when influenza viruses are known to be circulating in the communities surrounding the collaborating sites. Final determination for analysis will be made by group consensus.

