### ***Influenza vaccine effectiveness to prevent severe influenza***

Influenza vaccination is the most important public health strategy to prevent influenza illness and vaccination is recommended annually for all people aged 6 months or older in the United States. However, influenza VE varies from season to season, and across different age and risk groups. A growing body of research points to the effectiveness of influenza vaccination in preventing influenza-associated hospitalizations and other severe outcomes, such as admission to the ICU and in-hospital death. While these studies have begun to explore the benefits of vaccination in reducing the risk of influenza-related severe outcomes, with some studies suggesting that the vaccine is more effective in reducing severe disease than reducing infection, the data are largely inconclusive as most are insufficiently powered or not designed to examine and stratify VE by high-risk groups, including children, older adults and those with chronic conditions.

Of the recent studies, Thompson, et al., examined hospitalized adults over multiple influenza seasons found that influenza vaccination decreased influenza-related hospitalizations by 37%, and reduced ICU admission for influenza-related complications by 82%. Analysis of influenza-positive hospitalized adults in the United States also suggests 37% reduction in odds of ICU admission among those vaccinated for influenza. Similarly, studies have shown that influenza vaccination can decrease children's risk of admission to the pediatric intensive care unit by as much as 74% and influenza-associated mortality by 65%. Studies of influenza VE

among those at high risk for influenza-associated complications are rare, with the exception being pregnant women for whom several studies have demonstrated effectiveness of influenza vaccination against influenza infection during pregnancy and in the neonate.

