## 5.2 Participant Eligibility

Eligible individuals in each seasonal cohort will be those who can and would seek care for influenza at a healthcare facility within the network. Inclusion in the cohorts will be defined by each site based on enrollment information within the health system, allowing for  $\leq 30$  day administrative gaps, and care being sought within the system in the 12 months prior to the start of the influenza season. Individuals born in the 12 months prior to the start of the influenza season will be eligible for the cohorts as long as other inclusion criteria are met and no exclusion criteria are met.

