## **6.2 Sample Size**

Table 1 presents sample size requirements for the primary objective of VE against severe outcomes. Existing data from hospital-based surveillance was used to estimate the reported incidence of laboratory-confirmed hospitalizations, ICU admissions, and deaths. Data from the Behavioral Risk Factor Surveillance System (BRFSS) and National Health Interview Survey (NHIS) was used to estimate vaccine coverage.

For adults, we assumed vaccine coverage of 30% in adults aged 18-49 years, 42% in adults aged 50-64 years, and 65% in adults 65 years and older. We assumed a population made up of 33% of adults in each of the three age groups.

For children, we assumed vaccine coverage of 70% in children aged 6 months to 4 years and 50% in children aged 5 to 17 years. We assumed a population made up of 50% of children in each of the two age groups.

Table 1 Sample Size Estimations

|                              | Minimum Detectable VE | Person-years needed |             |
|------------------------------|-----------------------|---------------------|-------------|
|                              |                       | Adults              | Pediatrics  |
| VE against hospitalization   | 40%                   |                     | 398,319     |
|                              | 35%                   | 197,593             | 569,374     |
|                              | 30%                   | 292,719             | 842,278     |
|                              | 25%                   | 456,014             | 1.3 million |
|                              | 20%                   | 766,799             |             |
| VE against ICU admission     | 40%                   |                     | 1.01 m      |
|                              | 35%                   | 1.2 million         | 1.4 m       |
|                              | 30%                   | 1.8 m               | 1.9 m       |
|                              | 25%                   | 2.8 m               | 2.8 m       |
|                              | 20%                   | 4.8 m               |             |
| VE against in-hospital death | 40%                   |                     | 28.1 m      |
|                              | 35%                   | 5.4 m               | 39.4 m      |
|                              | 30%                   | 7.9 m               | 52.8 m      |

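### Observation starts on 1 September for every member, with no delayed entry for in-season births and no 6-month floor for VE; infant incidence is understated under criterion 5, and VE in young children is biased in a direction the protocol cannot settle

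*Protocol*

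**What the plan says.** **Clock.** Section 5.3: "Observation time for a given season will start on the day that influenza season begins, September 1 of each year". It applies to everyone: "Person-time at risk for influenza will be calculated for all individuals in the seasonal retrospective cohorts". The calculation is a plain subtraction: "The total observation time, person-time, is then the difference between the start and end of observation". The section lists reasons for ending observation early (death, disenrolment, moving away, end of season) but none for starting it late.

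**Who is admitted.** The opening of Section 5.2 says "Individuals born in the 12 months prior to the start of the influenza season will be eligible for the cohorts". Criterion 5, marked "For closed health systems only", goes further and admits a child who "was born and became a member during the 12 months prior to the start of or during the influenza season". Criteria 1 to 4 all need an encounter before the season, so those members are already born on 1 September. The exclusion criteria set no lower age limit.

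**Vaccination age.** Section 3.1 says "vaccination is recommended annually for all people aged 6 months or older in the United States". The paediatric sample size in Section 6.2 assumes coverage of "70% in children aged 6 months to 4 years" and gives none for younger infants. Objective 5 (Section 4.1) asks for VE against hospitalization at all ages.

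**Age variable and model.** Section 5.4 records age once, at the start of observation. Section 6.1 treats vaccination as time-varying and says that the confounders may include age and time in season.

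**The concern.** There are two separate problems.

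1. The start rule in 5.3 cannot be applied to a child who criterion 5 admits but who is not yet born on 1 September. Applied as written, it adds person-time in which no event can occur. That time enters the Objective 4 denominators and the unvaccinated arm of the Objective 5 cohort analysis. Recorded age is negative or undefined for these children.

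2. Infants under 6 months can contribute only unvaccinated time, or only unvaccinated cases and controls. They have no vaccinated counterpart of the same age. If their influenza hospitalization rate differs from that of older children in the same stratum, the vaccine contrast absorbs part of an age contrast.

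At stake are infant incidence and VE in the youngest children, one of the groups for whom Section 3.1 says existing VE evidence is insufficient.

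**Working it through.** The protocol gives no infant person-time to reproduce. The nearest stated figure, 398,319 paediatric person-years for a VE of 40% (Table 1), cannot be rebuilt because incidence, alpha and power are not given. Nothing below depends on it.

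**Step 1. Pre-birth time (criterion 5 only).** Assume uniform births and follow-up to 31 May; the season lasts 9 months.
- An in-season birth is counted for 9 months and observed for 4.5 on average. Incidence ratio: 4.5/9 = 0.5.
- All infants born in the 12 months before or the 9 months of the season, in birth-months × months:
  - counted: 12×9 + 9×9 = 189
  - actual: 12×9 + 9×4.5 = 148.5
  - ratio: 148.5/189 = 0.786, so incidence is understated by about 21%.

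The event count does not change, so this holds whatever the infant rate.

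**Step 2. Share of time under 6 months (criteria 1-4).** A child aged a months on 1 September (a < 6) spends 6 − a months of the season under 6 months. Summed over a from 0 to 6 this is 6²/2 = 18.
- Under 1 year: 18/12 = 1.5 of 9 months, about 17%.
- Under 2 years: 18/24 = 0.75 of 9 months, about 8%.

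**Step 3. Effect on cohort VE, children under 2 years.** Expected-value model of the season.
- From the protocol: coverage 70% (6.2); true VE 40% (a Table 1 row); vaccinated status two weeks after the dose (5.4).
- Assumed: uniform births; doses given on 1 November or on reaching 6 months, whichever is later; season flat or peaked around 1 February.
- R = rate under 6 months divided by rate at 6 months and over. The protocol gives no value, so R is varied.
- Calendar-adjusted Mantel-Haenszel rate ratio, RR = Σ(E_V·U/N) / Σ(E_U·V/N), where E is events, U and V are unvaccinated and vaccinated time, and N = U + V. VE = 1 − RR. Age within the stratum is not adjusted.

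Estimated VE (flat / peaked season), true value 40%:

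| R | Criteria 1-4 | Criterion 5, clock from 1 September |
|---|---|---|
| 0.5 | 36.6 / 36.1% | 5.4 / −0.4% |
| 1 | 40.0% | 26.4 / 22.3% |
| 2 | 45.8 / 46.6% | 49.0 / 46.5% |
| 3 | 50.7 / 51.9% | 61.0 / 59.2% |

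The R = 1 row isolates pre-birth time. It lowers VE by 40.0 − 26.4 = 13.6 to 40.0 − 22.3 = 17.7 points. Under criterion 5 the net bias turns upward only when R exceeds about 1.5 to 1.7.

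**Step 4. Candidate repairs.** Starting the clock at birth alone, under criterion 5, gives 40.0% at R = 1, about 59% at R = 2 and about 68% at R = 3. It cures the denominator but not the ineligible time. Starting at the later of 1 September, birth and 6 months of age returns 40.0% in every scenario run.

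**The case against.** **Scope.** Pre-birth time arises only under criterion 5, one of five candidate definitions, and only at closed systems. This stands: if criterion 5 is not adopted, the 21% does not arise. But the protocol plans to build that cohort, and its start rule does not fit it. The option in 5.3 to shorten the analysis window by consensus supplies no entry rule.

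**Detail for the analysis plan.** Age bands and a VE age floor are often set there, and sufficiently fine adjustment for age would remove the second bias. This stands in part. Section 6.1 does list age as a possible confounder. But age is fixed at the start of observation, so a child who turns 6 months in mid-season moves from ineligible to eligible with no change in the recorded covariate. The youngest band of under 2 years in Appendix C proves nothing here, because that is an example table for Objective 1.

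**Time-varying exposure.** Unvaccinated time before a dose is correct handling, not an error. This stands for children who are old enough to be vaccinated. It does not make infants who cannot be vaccinated comparable with them.

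**A stronger reading.** A reader might infer that both kinds of time inflate VE in young children. The documents do not support this. Pre-birth time is event-free and unvaccinated, so it lowers the unvaccinated rate and pulls VE down. Time under 6 months raises VE only if R exceeds 1, and no rate is given. Nor can upward bias be claimed for the test-negative analysis. There the direction depends on the ratio of cases to controls among infants, not on their hospitalization rate. Section 3.1 notes that RSV hospitalizes many young children; if young infants supply disproportionately many controls, the bias would be downward.

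**Conclusion.** The point holds as two defects of different standing.

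- **Certain from the text:** the start rule in 5.3, the opening of 5.2 and criterion 5 disagree on in-season births. Under criterion 5 the rule as written halves incidence for those births and understates it by about 21% across infants, given uniform births and follow-up to 31 May. It also pulls cohort VE in young children down.
- **Certain in mechanism, open in direction:** under all five definitions, infants under 6 months enter Objective 5 as necessarily unvaccinated. Under criteria 1-4, with a true VE of 40% in children under 2 years, the cohort estimate runs from about 36% (R = 0.5) through no bias (R = 1) to about 46% (R = 2) and 51-52% (R = 3).

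The VE figures are illustrative. They rest on the assumed infant rate, vaccination timing and season shape, and on age not being finely adjusted. The direction in the test-negative analysis is not established. Because the two effects can oppose each other, VE in young children would depend on which cohort definition is chosen, and Section 5.2 leaves that to consensus.

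**What to change.** 1. Reconcile the opening of Section 5.2 with criterion 5 on whether in-season births are admitted.
2. In Section 5.3, start observation at the later of 1 September, date of birth and, for in-season births under criterion 5, date of enrolment.
3. In Section 6.1, Objective 5, count person-time only from 6 months of age in the cohort analyses, and admit test-negative cases and controls only if aged at least 6 months.
4. In Objective 4, keep infants under 6 months and report them as a separate stratum.

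**Cost.** A few sentences, best settled before extraction. VE loses a small amount of unvaccinated infant person-time that has no vaccinated comparator. Sites must supply, or apply locally, date of birth or age in months. Section 5.4 lists only age at the start of observation, and the codebook is a separate file not at hand, so whether this is already planned cannot be confirmed.

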### **5.4 Exposures of Interest**

#### ***Vaccination status***

Within each annual retrospective cohort, an individual will be considered vaccinated for influenza if there is documented evidence of influenza vaccination and evidence that the vaccination was administered at least two weeks prior to an influenza-associated respiratory hospitalization (or influenza-associated ARI outpatient visit).

In order to assess influenza vaccination status, multiple sources will be queried, as available, including EHR, state/local vaccine registries, all-payer claims or other billing databases. For each available source, data will be provided on date of vaccination, type of vaccine administered, vaccination route, location of vaccination, vaccine lot number and number of vaccine doses (for children <9 years of age). Vaccination records will be considered as evidence of vaccination if there is at least a partial date (month and year). Children (aged <9 years) will be considered fully vaccinated for the current season if they received two doses, at least one month apart, during the current season or if they received one dose of the current season's vaccine and had at least two doses in prior seasons.

Network sites will provide information on number of sources queried for vaccine data and completeness of data by vaccine source. Because each site is querying multiple sources, a hierarchy of sources will be established for each site or through joint consensus with collaborating partners. For vaccination data extracted from EHRs, sites will provide information on how vaccination data was pulled (for example, through use of CPT or other codes).

For a subset of patients (number to be determined by joint consensus by the collaborating partners), accuracy of extracted vaccination data will be verified through manual review of source data (i.e. medical chart review).

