### ***Influenza and other respiratory virus testing***

Data on all influenza and other respiratory virus test results will be extracted for all members of the cohort during the surveillance period. For each test result, sites will provide data on encounter type associated with the lab test, diagnoses (based on ICD code) associated with encounter during which testing occurred, date of specimen collection, type of test performed and test result. Network sites will provide information on how laboratory testing data was pulled (for example, through use of CPT or other procedure codes or from laboratory databases). For a subset of patients (number to be determined by joint consensus by the collaborating partners), accuracy of extracted laboratory data will be verified through manual review of source data (i.e. medical chart review or review of laboratory databases). Respiratory viruses for which data will be collected, in addition to influenza, include respiratory syncytial virus, adenovirus, parainfluenza virus, human metapneumovirus, rhinovirus, enterovirus, coronaviruses, and other viruses, including novel viruses.

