**5.5 Outcomes of Interest**

- Respiratory illness-associated hospitalizations with laboratory-confirmed influenza
  - Respiratory hospitalizations will be defined using ICD-9 and ICD-10 discharge diagnoses codes as listed in Appendix D.
  - Data on all respiratory hospitalizations will be collected for the entirety of the surveillance period (influenza season).
  - The respiratory hospitalizations will be linked with data on influenza testing to determine if the hospitalization was associated with laboratory-confirmed influenza.
    - Laboratory-confirmed influenza associated respiratory hospitalization will be defined by a positive influenza test within 14 days prior to hospitalization or no more than 3 days after hospital admission.

- Hospitalization will be defined as admission to an inpatient ward or an observation unit. Time spent only in the emergency department will not count as a hospitalization.
- Re-admissions that occur within 30 days of the index hospitalization will be counted as part of the index hospitalization. Readmissions that occur >30 days after the index hospitalization will be considered new hospitalization events.
- ICU admission among persons hospitalized with laboratory-confirmed influenza-associated respiratory hospitalization
- Invasive mechanical ventilation among persons hospitalized with laboratory-confirmed influenza-associated respiratory hospitalization
- In-hospital death among persons hospitalized with laboratory-confirmed influenza-associated respiratory hospitalization
- Acute respiratory illness-associated outpatient visits with laboratory-confirmed influenza
  - Acute respiratory illness-associated outpatient visit will be defined using the ICD-9 and ICD-10 discharge codes listed in Appendix D.
  - Data on all acute respiratory illness-associated outpatient visits will be collected for the entirety of the surveillance period (influenza season).
  - The acute respiratory illness outpatient visit will be linked with data on influenza testing to determine if the visit was associated with a positive influenza laboratory test.

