***Objective 5: Assessment of vaccine effectiveness***

- We will estimate the effect of influenza vaccination on risk of lab-confirmed influenza-associated respiratory hospitalization by age group, influenza type/subtype, and high-risk conditions
  - The risk of influenza-associated respiratory hospitalization among cohort members who were or were not vaccinated with the current season influenza will be compared using appropriate methods for longitudinal data with time varying exposure, including Poisson regression or proportional hazards modeling.
  - VE will be estimated as  $(1 - \text{adjusted relative risk}) \times 100$ .
  - We will assess and adjust for confounders as appropriate. These may include characteristics such as age, sex, site, race/ethnicity, high-risk health conditions, prior healthcare utilization, time of event during the influenza season, etc.
  - Data collected for this study are intended to be pooled across sites. VE will first be estimated for each site and heterogeneity in estimated VE across sites examined.
- We will estimate the effect of influenza vaccination on risk of lab-confirmed influenza-associated ARI outpatient visit among children (adults only if influenza testing allows for this) by age group, influenza type/subtype, and high-risk conditions
  - The risk of influenza-associated outpatient visits among cohort members who were or were not vaccinated with the current season influenza will be compared using appropriate methods for longitudinal data with time varying exposure, including Poisson regression or proportional hazards modeling.
  - VE will be estimated as  $(1 - \text{adjusted relative risk}) \times 100$ .

- We will assess and adjust for confounders as appropriate. This may include characteristics such as age group, sex, site, race/ethnicity, high-risk health conditions, prior healthcare utilization, time of event during the influenza season, etc.
- Data collected for this study are intended to be pooled across sites. VE will first be estimated for each site and heterogeneity in estimated VE across sites examined.
- VE analyses against influenza-associated respiratory hospitalizations will also be conducted using a test-negative case-control design
  - This analysis will be conducted among individuals who were hospitalized for acute respiratory illness during the influenza season and who were tested for influenza.
  - Cases will be defined as hospitalized individuals who tested positive for influenza.

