  - Controls will be defined as hospitalized individuals who tested negative for influenza.
  - Influenza vaccination status will be determined for all cases and controls and the odds of vaccination will be compared using logistic regression.
  - VE will be estimated as  $(1 - \text{adjusted odds ratio}) \times 100$ .
  - We will assess and adjust for confounders as appropriate. This may include characteristics such as age group, sex, site, race/ethnicity, high-risk health conditions, prior healthcare utilization, time of event during the influenza season, etc.
  - Data collected for this study are intended to be pooled across sites. VE will first be estimated for each site and heterogeneity in estimated VE across sites will be examined.

Beyond the primary objectives listed here, additional analyses may be pursued and will be considered by the joint steering committee.

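### The two-week vaccination lag is counted back from admission, although the infection may be proven up to 14 days earlier, which slightly lowers VE against hospitalization

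*Protocol*

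**What the plan says.** Protocol Section 5.4 (Vaccination status) requires documented vaccination and "evidence that the vaccination was administered at least two weeks prior to an influenza-associated respiratory hospitalization (or influenza-associated ARI outpatient visit". The lag is thus tied to the outcome event: admission for the inpatient outcome, the visit for the outpatient outcome.

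Section 5.5 calls a respiratory hospitalization laboratory-confirmed when it is "defined by a positive influenza test within 14 days prior to hospitalization or no more than 3 days after hospital admission". The proof of infection can therefore precede the event from which the lag is counted.

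Section 6.1, Objective 5, uses this exposure in two analyses. The cohort analysis is to use "appropriate methods for longitudinal data with time varying exposure, including Poisson regression or proportional hazards modeling". For the test-negative analysis, "Influenza vaccination status will be determined for all cases and controls and the odds of vaccination will be compared using logistic regression". Neither gives another reference date. The two-week phrase under Objective 2 concerns the start of influenza circulation in a descriptive analysis and does not bear on this.

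Two data rules matter for the remedy. For every test, sites supply the "date of specimen collection, type of test performed and test result" (Section 5.4, testing). On vaccination dates, "Vaccination records will be considered as evidence of vaccination if there is at least a partial date (month and year".

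**The concern.** The usual purpose of a two-week lag is to avoid charging the vaccine with infections that began before it could act. The lag does this only if it is counted from a date no later than the proof of infection. Counted from admission, it shortens by one day for each day that the positive test precedes admission.

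The people affected are hospitalized cases with an earlier positive test and a recent dose. They enter as vaccinated failures, which pulls VE against hospitalization towards zero. The error is systematic, so pooling sites and seasons does not remove it. It arises while vaccination is still under way, and observation starts on September 1 (Section 5.3). Appendix E has sites derive data elements before sending them, so the rule as written would be programmed at each site.

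**Working it through.** **Step 1: day count.** Take admission as day 0 and two weeks as 14 days.

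- Section 5.4: counted as vaccinated if dose day v ≤ -14.
- Section 5.5: confirming test on day t, with -14 ≤ t ≤ +3.
- Gap from dose to positive test = t - v. Its minimum among people counted as vaccinated is t + 14.

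| Test day t | Shortest dose-to-test gap (days) | Dose days counted as vaccinated but under 14 days before the test |
|---|---|---|
| -14 | 0 | 14 |
| -10 | 4 | 10 |
| -7 | 7 | 7 |
| -3 | 11 | 3 |
| -1 | 13 | 1 |
| 0 | 14 | 0 |
| +3 | 17 | 0 |

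For a test k days before admission, the affected dose days run from -(13 + k) to -14, which is k days. A dose given after the positive test can never count. Tests on or after admission are unaffected.

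**Step 2: the two outcomes.** Suppose a dose on day -16, a positive outpatient visit on day -10 and admission on day 0. The dose is 6 days before the visit (unvaccinated for the outpatient outcome) and 16 days before admission (vaccinated for the hospitalization outcome). It is one infection.

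**Step 3: size.** The protocol gives no figure to reproduce, and it does not state the share of cases tested before admission, the lag or weekly uptake. All inputs here are assumptions:

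- s, share of cases with a pre-admission positive: 10-30%
- L, mean lag from test to admission: 3-10 days
- u, uptake: 1-5% of people per week
- 30% labelled vaccinated on the admission date; true VE 40% (risk ratio 0.6)
- a dose under 14 days old gives no protection

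The share of people whose dose falls in the affected window is x = u × L / 7. These people already belong to the 30% labelled vaccinated, and under time-varying exposure their person-time is counted there too. They contribute cases at full risk instead of 0.6 of it, so only the remaining 0.4 is excess:

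observed RR = [0.6 × (0.30 - s·x) + s·x] / 0.30 = 0.6 + 0.4 × s·x / 0.30

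| Scenario | s | L | u | x | s·x | RR | VE |
|---|---|---|---|---|---|---|---|
| Low | 0.10 | 3 | 0.01 | 0.0043 | 0.0004 | 0.6006 | 39.9% |
| Central | 0.20 | 5 | 0.03 | 0.0214 | 0.0043 | 0.6057 | 39.4% |
| High | 0.30 | 10 | 0.05 | 0.0714 | 0.0214 | 0.6286 | 37.1% |

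**Step 4: cross-check over follow-up.** With T the mean vaccinated person-days per person, observed VE = VE × (1 - s × L / T):

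- s = 0.1, L = 3, T = 200: 40 × (1 - 0.3/200) = 39.9%
- s = 0.3, L = 7, T = 120: 40 × (1 - 2.1/120) = 39.3%

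Both routes put the usual loss below one VE point.

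**The case against.** **Each outcome has its own anchor by design.** Section 5.4 names the outpatient visit separately, and under time-varying exposure a person may properly be unvaccinated at one event and vaccinated at a later one. This stands. A reader might infer that the rules contradict each other, or that inpatient and outpatient VE cannot be compared. The text does not support that. What remains is that the later label is attached to an infection already proven at the earlier date.

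**The effect is small and fades.** This stands. Once uptake slows, x approaches zero, and follow-up runs to May 31.

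**A reader might compute a much larger bias.** Moving the misclassified cases into the vaccinated group while leaving the groups at 0.30 and 0.70, RR = [(0.18 + s·x)/0.30] / [(0.70 - s·x)/0.70], gives VE of 39.8%, 38.2% and 30.7% for the three scenarios. That moves the cases without their person-time (or the matching controls), so it overstates the loss. The Step 4 formula also reaches 30.7%, but only if every case is tested 14 days early and vaccinated follow-up averages 60 days: 40 × (1 - 14/60). Nothing in the protocol supports those inputs.

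**Same-day vaccination and infection is the extreme corner.** This stands. It needs dose and test both exactly on day -14. Nor does the protocol say that a dose under 14 days old gives no protection. If it gives some, the bias is smaller still.

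**This could be left to an analysis plan.** It could if the protocol were silent, but Section 5.4 fixes the anchor and Objective 5 does not override it.

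**Conclusion.** The point holds as a small, correctable fault in a stated definition. Read together, Sections 5.4 and 5.5 let doses given 0 to 13 days before proven infection count as vaccinated, and no other section supplies a different anchor.

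The day count rests on the protocol alone. The direction, towards lower VE against hospitalization, also requires that recent doses protect less than older ones. The size rests wholly on the assumed inputs: a true 40% reads 39.4% centrally and 37.1% at the high end while uptake is ongoing, with a smaller loss over a full season. This would not change the broad reading of a VE estimate. It deserves correction because the error is systematic and the specimen date is already collected.

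**What to change.** In Section 5.4, count the two weeks back from the earlier of the qualifying specimen collection date and the admission (or outpatient visit) date. Apply the same rule to test-negative controls, using each control's own qualifying specimen. The shortest dose-to-positive gap among fully dated records then rises from 0 to 14 days. State how doses 0 to 13 days before that date are handled.

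Keep admission as the event date in the cohort models. Dating the event by the specimen could place an early-September admission before observation begins (Section 5.3) and would detach it from the admission-based 30-day readmission rule (Section 5.5).

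The cohort models need one safeguard. Person-time without an event has no specimen date, so relabelling cases alone would move the numerator without its denominator. With the high inputs that gives RR = [0.6 × (0.30 - 0.0214)/0.30] / [(0.70 + 0.0214)/0.70] = 0.541, a VE of 45.9%, which is further from 40% than the present rule. One way to keep the two aligned is to make days 14 to 27 after a dose a separate exposure level for everyone. Under Section 5.5's limit, only those days can hide a gap under 14 days.

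The cost is a sentence or two in Section 5.4 and some derivation work, with specimen, admission and encounter dates already extracted. A separate exposure level would also take some person-time out of the main contrast. Records with only month and year of vaccination remain imprecise under either anchor.
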